**Table 2. Analysis Time Windows for HCV RNA and Resistance Endpoints (Post-Treatment Period)**

Scheduled Visit a	Nominal Day (Study Drug End Day)	Time Window (Study Drug End Day Range)
Post-Treatment Week 4	28	3 to 56
Post-Treatment Week 12	84	57 to 126
Post-Treatment Week 24	168	127 to 999
SVR 4 b	28	3 to 56
SVR 12 b	84	57 to 126
SVR 24 b	168	127 to 210

a. Post-Treatment Visits are applicable for subjects who received at least one dose of study drug.

b. For SVR windows, the last value in the window will be used.

Note: The result closest to the scheduled time point will be used, except for SVR4, SVR12, and SVR24. For all windows, data must occur after Study Drug End Day 2. Study Drug End Day 0 is defined as the day of the last dose of study drug.

**Table 3. Analysis Time Windows for Safety Laboratory and Vital Sign Measurements, Child Pugh Scores and PRO Instruments (Post-Treatment Period)**

Scheduled Visit a	Nominal Day (Study Drug End Day)	Time Window (Study Drug End Day Range)
Post-Treatment Week 4	28	3 to 56
Post-Treatment Week 12	84	57 to 126
Post-Treatment Week 24	168	127 to 999
Final Post-Treatment Visit b	> 2 days after last dose of study drug	

a. Post-Treatment Visits are applicable for subjects who received at least one dose of study drug.

b. The last value within the Post-Treatment Period window will be used to define the Final Post-Treatment visit value. The lower bound of this Final window is Study Drug End Day 3. Study Drug End Day 0 is defined as the day of the last dose of study drug.

Note: The result closest to the scheduled time point will be used. For all windows, data must occur after Study Drug End Day 2. Vital signs are collected at every post-treatment visit; hematology, chemistry and coagulation panels are collected at PTW4 or PT D/C (if subject discontinued prior to PTW4). PRO instruments and Child Pugh Scores are collected at PTW12 and PTW24 (or PT D/C).

## **6.3 Missing Data Imputation**

### **Missing Data Imputation for SVR**

HCV RNA values will be selected for analysis based on the analysis windows defined in Section 6.2.

For analyses of SVR, subjects missing visit values will have backward imputation applied, if possible. For backward imputation, if the nearest HCV RNA value after the SVR window is unquantifiable or undetectable, then it will be used to impute the HCV RNA value in the SVR window. If a subject is missing an HCV RNA value within the appropriate SVR window after performing backward imputation, then this value will be imputed with an HCV RNA value from a local laboratory if present; otherwise, the HCV RNA value will be missing. Subjects with missing HCV RNA data in the analysis window, after imputations, will be imputed as a failure.

Regardless of the imputation method described above, if a subject starts another treatment for HCV, then all HCV RNA values for this subject measured on or after the start date of the new HCV treatment will be excluded from analyses. The subject will be considered a failure for summaries of viral response at all time points after the start of the new HCV treatment.

### **Missing Data Imputation for Virologic Failure**

If HCV RNA values from the central laboratory are missing but a local laboratory value is present in the appropriate time period, then the local laboratory value will be used to assess post-treatment relapse and on-treatment virologic failure.

### **Missing Data Imputation for PRO Questionnaires**

If a respondent answers at least 50% of the items in a multi-item scale of the Kidney Disease Quality of Life (KDQOL-36), the missing items will be imputed with the average score of the answered items in the same scale. In cases where the respondent did not answer at least 50% of the items, the score for that domain will be considered missing.

If a subject starts another treatment for HCV, then all PRO assessment values for this subject measured on or after the start date of the new HCV treatment will be excluded from analyses.

## **7.0 Demographics, Baseline Characteristics, Medical History, and Other Medications**

The ITT population will be used to summarize demographics, baseline characteristics, medical history and previous, concomitant, and post-treatment medications; data will be summarized across all subjects and by assigned treatment arm.

### **7.1 Demographic and Baseline Characteristics**

Categorical demographic and baseline characteristic variables will be summarized with the number and percentage of subjects in each category. Continuous variables will be summarized with descriptive statistics (number of non-missing observations, mean, standard deviation, median, maximum and minimum). For categorical variables, the number of missing observations will be displayed, if applicable, on the summary tables. Percentages will be calculated based on the number of non-missing observations.

Continuous demographic and baseline characteristics include age, weight, height, body mass index (BMI), baseline  $\log_{10}$  HCV RNA level, creatinine clearance (Cockcroft-Gault calculation), eGFR (using the modification of diet in renal disease [MDRD] formula), platelet count, albumin, GGT, APRI, FIB-4, AST, ALT, and total, direct and indirect bilirubin.

Categorical demographic and baseline characteristics include:

- Age (< 65 or  $\geq$  65 years) and (< 75 or  $\geq$  75 years);
- Sex (male or female);
- Race and black race: black or non-black;
- Ethnicity (Hispanic or Latino, Not Hispanic or Latino);
- Geographic region (North America, Europe, or rest of world);

- Country;
- Baseline BMI ( $< 30$  or  $\geq 30$  kg/m^2);
- HCV genotype and subtype (using central laboratory results and final genotype/subtype results, see Section 10.8);
- Prior HCV treatment history (naïve or experienced);
- For treatment-experienced subjects, type of previous regimen (IFN- or SOF-based);
- Baseline cirrhosis status (yes/no);
- For cirrhotic subjects, Baseline Child-Pugh score (5, 6, or  $> 6$ );
- Chronic Kidney Disease stage at screening (Stage 3b, Stage 4, Stage 5 without dialysis, or Stage 5 requiring dialysis);
- For treatment-experienced subjects, type of non-response to previous treatment (on-treatment non-responder, breakthrough, post-treatment relapse, or unknown/other);
- Baseline HCV RNA level ( $< 1,000,000$ ;  $\geq 1,000,000$  to  $< 2,000,000$ ; or  $\geq 2,000,000$  IU/mL);
- Baseline platelet count ( $< 90$  or  $\geq 90 \times 10^9/L$ );
- Baseline albumin ( $< 35$  or  $\geq 35$  g/L);
- Baseline eGFR ( $< 15$ ,  $\geq 15$  to  $< 30$ ,  $\geq 30$  to  $< 45$ , or  $\geq 45$  mL/min/1.73 m^2);
- Baseline creatinine clearance ( $< 15$ , or  $\geq 15$  mL/min);
- Baseline fibrosis stage (equivalent to Metavir F0 – F1, F2, F3, or F4);
- Concomitant use of Proton Pump Inhibitors (PPIs);
- Concomitant use of Statins (yes/no);
- Dialysis at screening (yes/no);
- For dialysis subjects, type of dialysis (hemodialysis, peritoneal dialysis, or other);
- Tobacco use (user, ex-user, or non-user);
- Alcohol use (drinker, ex-drinker, or non-drinker);
- Injection drug use (yes, within last 12 months; yes, more than 12 months ago; or no);

- Use of stable opiate substitution (yes/no);
- History of diabetes (yes/no);
- History of depression or bipolar disorder (yes/no);
- History of bleeding disorders (yes/no);
- History of cardiovascular disease (yes/no);
- History of hypertension (yes/no);

Summaries of baseline resistance are described in Section 10.8.

For TE subjects, any regimen that contains SOF with or without IFN or RBV is SOF-based. Otherwise, any regimen that contains IFN with or without RBV is IFN-based.

Any concomitant medication coded to the WHO Drug Dictionary ATC code of A02BC will be counted as a PPI. Any concomitant medication coded to the WHO Drug Dictionary ATC code of C10AA or C10BX will be counted as a statin.

CKD categorization at screening is defined according to eGFR and requirement of dialysis in Table 4 below:

**Table 4. Definition of Chronic Kidney Disease Stages**

CKD Stage	eGFR (mL/min/1.73 m  )*
3b	30 to < 45
4	15 to < 30
5	< 15 or requiring dialysis

\*  $eGFR (mL/min/1.73 m^2) = 175 \times (\text{Serum Creatinine})^{-1.154} \times \text{Age}^{-0.203} \times (0.742 \text{ if female}) \times (1.21 \text{ if black})$ .

Dialysis at screening is defined as any dialysis that started prior to the Day 1 visit based on the eCRF "Dialysis Treatment Prior to and Initiated During Study." For subjects requiring dialysis, hemodialysis is defined as intermittent hemodiafiltration, intermittent hemodialysis, intermittent hemofiltration, continuous RRT, or sustained low efficiency (daily) dialysis; peritoneal dialysis is defined as automated peritoneal dialysis or continuous ambulatory peritoneal dialysis.

Baseline fibrosis stage is defined for subjects with non-missing liver biopsy scores, FibroScan scores, or FibroTest scores. Only one score will be used to categorize each subject even if a subject has more than one score recorded. If a biopsy score is present, then it will be used to categorize the subject, regardless of the FibroScan/FibroTest score. Similarly, if a FibroScan score is present along with a FibroTest score, then the FibroScan score will be used to categorize the subject. If biopsy and FibroScan scores are not present and more than one FibroTest result is available, then the baseline FibroTest result (i.e., last non-missing FibroTest result on or before Day 1) will be used to categorize the subject. Subjects will be categorized as F0 – F1, F2, F3 or F4 according to [Table 5](#).

**Table 5. Baseline Fibrosis Stage**

Baseline Fibrosis Stage, Metavir Equivalents	Liver Biopsy Metavir, Batts Ludwig, Knodell, IASL, Scheuer, or Laennec Score	Liver Biopsy Ishak Score	FibroScan (kPa)	FibroTest*
F0 – F1	0 or 1	0, 1, or 2	< 8.8	≤ 0.48
F2	2	3	≥ 8.8 to < 9.6	0.49 to 0.58
F3	3	4	≥ 9.6 to < 12.5	0.59 to 0.74
F4	4	≥ 5	≥ 12.5	≥ 0.75

\* APRI will not be used to derive baseline Fibrosis Stage. However, per inclusion/exclusion criteria, subjects need to have concordant FibroTest and APRI scores in order to determine eligibility.

The central laboratory calculates the estimated creatinine clearance (CrCl) based on the following Cockcroft-Gault formula:

$$\text{CrCl (mL/min)} = [(140 - \text{age}) \times (\text{weight in kg}) \times (0.85 \text{ if female})] / [(\text{serum creatinine (mg/dL)} \times 72)].$$

The central laboratory calculates the eGFR by MDRD based on the following formula:

$$\text{eGFR (mL/min/1.73 m}^2\text{)} = 175 \times (\text{Serum Creatinine})^{-1.154} \times (\text{Age})^{-0.203} \times (0.742 \text{ if female}) \times (1.212 \text{ if African American}).$$

Baseline APRI and FIB-4 are calculated by the equations below. Subjects who do not have concurrent AST and platelet values at baseline will be excluded from the summary of baseline APRI. Age is defined in years at baseline. Subjects who do not have concurrent values of AST, ALT and platelet count at baseline or subjects who are missing age will be excluded from the summary of FIB-4.

$$\text{APRI} = \frac{\frac{\text{AST Level (U/L)}}{\text{AST (Upper Limit of Normal)(U/L)}}}{\text{Platelet Count (10}^9\text{/L)}} \times 100$$

$$\text{FIB-4} = \frac{\text{Age (years)} \times \text{AST Level (U/L)}}{\text{Platelet Count (10}^9\text{/L)} \times \sqrt{\text{ALT (U/L)}}}$$

Presence or absence of cirrhosis will be determined as collected in IRT/EDC ("subject's cirrhosis status?" – "Compensated cirrhotic" or "Non-cirrhotic").

Baseline Child-Pugh score is determined by the Day 1 assessment of ascites and hepatic encephalopathy along with the baseline values of total bilirubin, serum albumin, and international normalized ratio (INR). The Child-Pugh score is the sum of the points assigned for each of the five observed findings as defined in [Table 6](#).

**Table 6. Child-Pugh Classification of Severity of Cirrhosis**

Parameter	Points Assigned for Observed Findings		
	1	2	3
Total bilirubin, $\mu\text{mol/L}$ (mg/dL)	< 34.2 (< 2)	34.2 – 51.3 (2 – 3)	> 51.3 (> 3)
Serum albumin, g/L (g/dL)	> 35 (> 3.5)	28 – 35 (2.8 – 3.5)	< 28 (< 2.8)
INR	< 1.7	1.7 – 2.3	> 2.3
Ascites*	None	Slight	Moderate to severe
Hepatic encephalopathy**	None	Grade 1 or 2 (or suppressed with medication)	Grade 3 or 4 (or refractory to medication)

Child-Pugh category A: 5 – 6 points; Child-Pugh category B: 7 – 9 points; Child-Pugh category C: 10 – 15 points

\* None;

Slight ascites = Ascites detectable only by ultrasound examination;

Moderate ascites = Ascites manifested by moderate symmetrical distension of the abdomen;

Severe ascites = Large or gross ascites with marked abdominal distension.

\*\* None: normal consciousness, personality, neurological examination, electroencephalogram;

Grade 1: restless, sleep disturbed, irritable/agitated, tremor, impaired handwriting, 5 cps waves;

Grade 2: lethargic, time-disoriented, inappropriate behavior, asterixis, ataxia, slow triphasic waves;

Grade 3: somnolent, stuporous, place-disoriented, hyperactive reflexes, rigidity, slower waves;

Grade 4: unarousable coma, no personality/behavior, decerebrate, slow 2 to 3 cps delta activity.

Histories of diabetes, bleeding disorders, depression or bipolar disorder, hypertension, and cardiovascular disease will be based on the Medical/Surgical History eCRF, as defined in Table 7.

**Table 7. Medical/Surgical History eCRF**

Medical/Surgical History eCRF		
Subgroup	Body System	Condition/Diagnosis
Diabetes	Metabolic	Diabetes mellitus
Bleeding disorders	Blood	Clotting/bleeding problems Factor deficiency Hemophilia Von Willebrand disease
Depression or bipolar disorder	Neurologic and Psychiatric System	Bipolar disorder Depression
Cardiovascular disease	Cardiovascular	Angina Cardiac arrhythmia Cardiovascular disease Congenital heart disease Congestive heart failure Coronary artery disease Hypertension Myocardial infarction Myocarditis Peripheral vascular disease-arterial Peripheral vascular disease-venous Valvular heart disease Vasculitis
Hypertension	Cardiovascular	Hypertension

## 7.2 Medical History

Medical history data will be summarized and presented using body systems and conditions/diagnoses as captured on the eCRF. The body systems will be presented in alphabetical order and the conditions/diagnoses will be presented in alphabetical order within each body system. The number and percentage of subjects with a particular condition/diagnosis will be summarized. Subjects reporting more than one condition/diagnosis within a body system will be counted only once for that body system.

### **7.3 Prior, Concomitant and Post-Treatment Medications**

A prior medication is defined as any medication taken prior to the date of the first dose of study drug (GLE/PIB). A concomitant medication is defined as any medication that started prior to the date of the first dose of study drug and continued to be taken on or after the first dose of study drug or any medication that started on or after the date of the first dose of study drug, but not after the date of the last dose of study drug. A post-treatment medication for the treatment of HCV is defined as any medication taken on or after the last dose of study drug and entered as "Post-treatment HCV medications" on the eCRF.

The number and percentage of subjects taking prior medications, concomitant medications, and post-treatment HCV medications will be summarized by generic drug name based on the WHO Drug Dictionary. The prior HCV medications taken by treatment experienced subjects and collected on the "Last Prior HCV Therapy" and "Second to Last Prior HCV Therapy" eCRFs will be summarized separately from other prior medications, and will not be included in the summary of all prior and concomitant medication.

## **8.0 Subject Disposition**

The number and percentage of subjects who screen failed for any reason will be summarized for subjects who screen failed and by each screen fail reason.

### **8.1 Disposition of Safety Population**

The number of subjects in each of the following categories will be summarized by investigator for each treatment arm and overall.

- Enrolled subjects;
- Subjects who took at least one dose of study drug;
- Subjects who completed study drug;
- Subjects who prematurely discontinued study drug;

- Subjects who completed the study;
- Subjects who prematurely discontinued from the study;
- Subjects ongoing in the Post-Treatment Period (if applicable at the time of analysis).

The number and percentage of subjects who discontinued study drug will be summarized by reason (all reasons) and by primary reason (per eCRF) for each treatment arm and overall. Similar summaries will be provided for discontinuations from the study.

The number and percentage of subjects with reported study drug interruptions will be summarized by treatment arm. Reasons for study drug interruptions will be presented in the CSR listings.

## **9.0 Study Drug Exposure and Compliance**

Exposure and compliance will be summarized on the ITT population by treatment arm and overall.

### **9.1 Exposure**

The duration of exposure to study drug will be summarized for each treatment arm and overall in the safety population. Duration of exposure is defined for each subject as the last study drug dose date minus the first study drug dose date plus 1 day.

During each treatment period, descriptive statistics (mean, standard deviation, median, minimum, and maximum) will be presented for exposure. Study drug duration will also be summarized with frequencies and percentages using the following categories:

- 1 to 15 days
- 16 to 30 days
- 31 to 45 days
- 46 to 60 days
- 61 to 75 days

- 76 to 90 days
- 91 to 105 days
- > 105 days

In addition, the number and percentage of subjects with study drug duration of  $\geq 52$  days for Arm A,  $\geq 77$  days for Arm B and  $\geq 103$  days for Arm C will be summarized.

## **9.2 Compliance**

For each kit, the total number of tablets dispensed and returned is recorded. The compliance for study drug (glecaprevir/pibrentasvir) during the Treatment Period will be calculated as the percentage of tablets taken relative to the total tablets expected to be taken. The total number of tablets expected to be taken will be equal to the total number of tablets that should have been taken per the protocol for the duration that the subject was in the Treatment Period (date of last dose of study drug – date of first dose of study drug + 1). Study drug interruptions recorded on the eCRF will not be subtracted from the duration.

A subject is considered to be compliant if the percentage is between 80% and 120%. Compliance will be calculated for each subject and summarized with the mean, median, standard deviation, minimum, and maximum by treatment arm. A listing of compliance for each subject will be provided. The percentage of compliant subjects will be summarized for each treatment arm based on data as observed.

## **10.0 Efficacy Analysis**

### **10.1 General Considerations**

#### **General Considerations**

All efficacy analyses will be performed on the ITT population, unless otherwise specified.

Missing data will be imputed as described in Section 6.3 for analyses of the HCV RNA endpoints of SVR.

Plasma HCV RNA levels will be determined for each sample collected by the central laboratory using the Roche COBAS® AmpliPrep/COBAS® TaqMan® HCV Quantitative Test, v2.0. The lower limit of detection (LLOD) and lower limit of quantification (LLOQ) for this assay (regardless of genotype) are both 15 IU/mL.

HCV RNA results that are detectable but not quantifiable are reported as "< 15 IU/ML HCV RNA DETECTED" and those that are undetectable are reported as "HCV RNA NOT DETECTED" in the database.

The notation "HCV RNA < LLOQ" is used to represent all HCV RNA values < 15 IU/mL, including values reported as "HCV RNA NOT DETECTED" or "< 15 IU/ML HCV RNA DETECTED." HCV RNA  $\geq$  LLOQ are all quantifiable values of 15 IU/mL or greater.

### **Definitions for Efficacy Endpoints**

A confirmed quantifiable value during treatment is defined as any two consecutive HCV RNA measurements  $\geq$  LLOQ (or 100 IU/mL for **Breakthrough**), either both during treatment or at the final treatment measurement and the next consecutive post-treatment measurement. A confirmed quantifiable post-treatment value is defined as any two consecutive post-treatment HCV RNA measurements  $\geq$  LLOQ.

**Breakthrough** = confirmed HCV RNA  $\geq$  100 IU/mL after HCV RNA < LLOQ during the Treatment Period; or confirmed increase from nadir in HCV RNA (two consecutive HCV RNA measurements  $>$  1 log10 IU/mL above nadir) at any time point during the Treatment Period. A single breakthrough value ( $\geq$  100 IU/mL or  $>$  1 log10 above nadir) followed by lost to follow-up also will be considered a breakthrough (i.e., will not require confirmation).

**EOT failure** = HCV RNA  $\geq$  LLOQ at end of treatment with at least 6 weeks of treatment, where the HCV RNA value must be collected on or after Study Drug Day 36 and study drug duration  $\geq$  36 days.

**On-treatment virologic failure = Breakthrough or EOT failure;** if a subject meets both definitions of Breakthrough and EOT failure, he or she will be categorized as Breakthrough only.

**SVR4** = HCV RNA < LLOQ in the SVR4 window (4 weeks after the last actual dose of active study drug) without any confirmed quantifiable ( $\geq$  LLOQ) post-treatment value before or during that SVR window.

**SVR12** = HCV RNA < LLOQ in the SVR12 window (12 weeks after the last actual dose of active study drug) without any confirmed quantifiable ( $\geq$  LLOQ) post-treatment value before or during that SVR window.

**SVR24** = HCV RNA < LLOQ in the SVR24 window (24 weeks after the last actual dose of active study drug) without any confirmed quantifiable ( $\geq$  LLOQ) post-treatment value before or during that SVR window.

**Relapse12** = confirmed HCV RNA  $\geq$  LLOQ between end of treatment and 12 weeks after last actual dose of active study drug (up to and including the SVR12 window) for a subject with HCV RNA < LLOQ at Final Treatment Visit who completed treatment, excluding reinfection as described below.

**Relapse24** = confirmed HCV RNA  $\geq$  LLOQ within the SVR24 window for a subject who achieved SVR12 and has HCV RNA data available in the SVR24 window, excluding reinfection.

**Relapseoverall** = confirmed HCV RNA  $\geq$  LLOQ between end of treatment and up to and including the last HCV RNA measurement collected in the PT Period for a subject with HCV RNA < LLOQ at Final Treatment Visit who completed treatment, excluding reinfection.

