### **5.1.2 Modified Intention-to-Treat (mITT) Populations**

Sensitivity analyses of SVR12 as described in Section 10.5 will be performed on the ITT population modified to exclude subjects who did not achieve SVR12 for reasons other than virologic failure (mITT-VF).

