#### **Final Treatment Value**

The final treatment value is defined as the last non-missing measurement collected after Study Day 1 and on or before Study Drug End Day 2.

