### **6.2 Definition of Analysis Windows**

For efficacy analyses of HCV RNA, the time windows specified in [Table 1](#) and [Table 2](#) describe how efficacy data are assigned to protocol-specified time points during the Treatment and Post-Treatment Periods, respectively. All time points and corresponding time windows are defined based on the date/time of blood sample collection.

For safety laboratory data, PRO data, Child Pugh score and vital sign data, the time windows specified in [Table 1](#) and [Table 3](#) describe how data are assigned to protocol-specified time points.

If more than one assessment is included in a time window, the assessment closest (except in analyses of SVR) to the nominal time will be used. If there are two observations equally distant to the nominal time, the latest one will be used in analyses. For analyses of SVR (e.g., SVR12), the last value in the window will be used.

If multiple measurements are made on the same day for a safety laboratory parameter or a vital sign parameter, the average of the values will be used to calculate descriptive statistics and in analyses of the mean change from baseline. For summaries of shifts from baseline and potentially clinically significant values, multiple values on the same day will not be averaged; all values will be considered for these analyses.

**Table 1. Analysis Time Windows for HCV RNA and Resistance Endpoints, Safety Laboratory and Vital Sign Measurements, Child Pugh Scores and PRO Instruments (Treatment Period)**

Scheduled Visit	Nominal Day (Study Day)	Time Window (Study Day Range)
Day 1/Baseline a	1	≤ 1 a
Week 4	28	2 to 42
Week 8	56	43 to 70
Week 12 b,c	84	71 to 98
Week 16 c	112	99 to 126
Final Treatment Visit d	2 to ≤ 2 days after last dose of study drug	

a. Day of first dose of study drug.

b. For 12-week and 16-week treatment duration only.

c. For 16-week treatment duration only.

d. The last value within the window will be used to define the Final Treatment Visit value. The upper bound of this Final window is Study Drug End Day 2. Study Drug End Day 0 is defined as the day of the last dose of study drug.

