**Virologic failure for SVR12 = On-treatment virologic failure or Relapse12**

Only subjects who have at least one post-treatment HCV RNA value will be included in analyses of relapse. For the analysis of relapse, completion of treatment is defined as a study drug duration of 52 days or greater for Arm A, 77 days or greater for Arm B, and 103 days or greater for Arm C. If the last available post-treatment value is  $\geq$  LLOQ, then the subject will be considered a relapse (i.e., will not require confirmation).

HCV reinfection is defined as confirmed HCV RNA  $\geq$  LLOQ after the end of active treatment in a subject who had HCV RNA  $<$  LLOQ at Final Treatment Visit, along with the post treatment detection of a different HCV genotype, subtype, or clade compared with baseline, as determined by phylogenetic analysis of the NS3 or NS5A, and/or NS5B gene sequences. Reinfection in the case of the same HCV subtype is defined as a clade switch, as indicated by the lack of clustering between the baseline and post-treatment sequences by phylogenetic analysis. If phylogenetic analysis is not possible due to technical difficulties, HCV reinfection may be determined with a confirmed HCV genotype or subgenotype switch by the Versant HCV Genotype Inno-LiPA Assay v2.0 or Sanger assay.

Post-treatment relapse is defined as described earlier (**Relapse12**, **Relapse24**, **Relapseoverall**), and no genotype, subtype, or clade switch compared with baseline as determined by phylogenetic analysis of the NS3 or NS5A gene sequences. If phylogenetic analysis is not possible due to technical difficulties, the subject will be defined as having a post-treatment relapse unless an HCV genotype or subtype switch is confirmed by the Versant HCV Genotype Inno-LiPA Assay v2.0 or Sanger assay.

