### **Reasons for SVR12 Non-Response**

Subjects who do not achieve SVR12 (SVR12 non-responders) will be categorized as having:

1. On-treatment virologic failure (see **On-treatment virologic failure** definition);
2. HCV reinfection (see definition described earlier);
3. Relapse12;

4. Prematurely discontinued study drug with no on-treatment virologic failure (defined as any SVR12 non-responder who prematurely discontinued study drug [study drug duration < 52 days for Arm A, < 77 days for Arm B, and < 103 days for Arm C] and did not meet the **On-treatment virologic failure or reinfection** definitions);
5. Missing follow-up data in the SVR12 window (defined as any subject who completed study drug without data in the SVR12 window after applying the imputation rules and not meeting the definitions of [1], [2], [3], or [4]);
6. Other (defined as any SVR12 non-responder not meeting the definitions of [1] – [5]).

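### EOT failure and Relapse12 read end-of-treatment status from different samples, so a rare completer with observed virologic failure is counted in neither secondary endpoint and leaves mITT-VF

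*SAP*

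**What the plan says.** All references are to the SAP.

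- **EOT failure** (10.1, Definitions for Efficacy Endpoints) is HCV RNA ≥ LLOQ at end of treatment, "where the HCV RNA value must be collected on or after Study Drug Day 36 and study drug duration" is at least 36 days.
- **Relapse12** (same place) is confirmed post-treatment HCV RNA ≥ LLOQ in a subject with HCV RNA below "LLOQ at Final Treatment Visit who completed treatment, excluding reinfection as described below". Reinfection carries the same Final Treatment Visit condition.
- **Final treatment value** (6.1.2) is "the last non-missing measurement collected after Study Day 1 and on or before Study Drug End Day 2". Table 1 agrees: "The last value within the window will be used to define the Final Treatment Visit value". Neither place sets a Day 36 floor.
- **Completion** (10.1) rests on drug duration alone: "completion of treatment is defined as a study drug duration of 52 days or greater for Arm A, 77 days or greater for Arm B". The Arm C threshold is 103 days. No end-of-treatment sample is needed.
- **Reasons for SVR12 non-response** (10.1) end with a residual category, Other, for any "non-responder not meeting the definitions of [1] – [5"].
- **mITT-VF** (5.1.2) drops subjects who missed SVR12 "for reasons other than virologic failure (mITT-VF").

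**The concern.** On-treatment failure and relapse are the two secondary endpoints, and together they define virologic failure for SVR12. Among completers who are viraemic after treatment, and apart from reinfection, they should leave no gap. They do leave one, because one definition rejects an early sample and the other accepts it.

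The effect is asymmetric. Take a completer whose only on-treatment sample is from Day 28. If it is < LLOQ, later viraemia is Relapse12. If it is 40 IU/mL, the same later viraemia is neither Relapse12 nor EOT failure. The subject with the poorer documented response is the one who leaves the failure count.

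The error can act in one direction only: it lowers the secondary failure counts and virologic failure through Post-Treatment Week 12, and it raises SVR12 in mITT-VF.

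**Working it through.** **The plan's own figure.** Section 4.3 gives a half-width of 0.031 for 97% of 120. 1.96 × √(0.97 × 0.03 / 120) = 0.0305, which agrees to rounding. The point does not depend on it, but 3% of 120 is 3.6, so only about 4 non-responders of any kind are implied.

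**Tracing one subject.** Arm A, 56 days of drug, Day 28 value 40 IU/mL, no Week 8 sample (or one drawn on Study Drug End Day 3 or later, which Table 2 treats as post-treatment), and HCV RNA ≥ LLOQ at Post-Treatment Weeks 4 and 12.

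1. Breakthrough: not met. There is no earlier value < LLOQ, and the Day 28 value is itself the nadir.
2. EOT failure: not met. The sample precedes Day 36.
3. Reinfection and Relapse12: not met. The Final Treatment value is not < LLOQ.
4. Premature discontinuation: not met, since 56 ≥ 52 days.
5. Missing follow-up data: not met, since the SVR12 window has a value.
6. Other: the only category left, so the subject is excluded from mITT-VF.

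**Variations under the same rules** (viraemic at Post-Treatment Weeks 4 and 12 unless stated):

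| On-treatment values | Category |
|---|---|
| Day 28 = 40, none later; Arm A, B or C completer | Other |
| Day 35 = 40, none later | Other |
| Day 37 = 40, none later (still in the Week 4 window, Days 2–42) | EOT failure |
| Day 28 < LLOQ, none later | Relapse12 |
| Day 28 = 40, Week 8 = 40 | EOT failure |
| Day 28 = 40, Week 8 < LLOQ | Relapse12 |
| Day 28 = 40, none later; viraemic at Post-Treatment Week 4, SVR12 window empty | Missing follow-up data |

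**How often.** The SAP caps compensated cirrhosis at about 30 of 120, so Arm A has at most about 90 if that cap is filled, less treatment-experienced GT3 subjects. The SAP gives none of the following rates; they are assumptions.

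- No sample from Day 36 to End Day 2: 5 to 10%. Of those, ≥ LLOQ at Week 4: 5 to 20%.
- Exposed to the gap: 90 × 0.05 × 0.05 = 0.2 to 90 × 0.10 × 0.20 = 1.8 subjects.
- Misclassified, if 3% of them fail (the complement of the planning rate): 0.225 × 0.03 = 0.007 to 1.8 × 0.03 = 0.054.
- Misclassified, if 20% of these slow responders fail: 0.225 × 0.20 = 0.05 to 1.8 × 0.20 = 0.36.

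**Effect of one such subject.** Wilson limits are [p + z²/2n ± z√(p(1−p)/n + z²/4n²)] / (1 + z²/n), with z = 1.96.

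| Result | As written | Subject counted |
|---|---|---|
| Virologic failure, no others | 0/120: 0% (0 to 3.1%) | 1/120: 0.83% (0.15 to 4.6%) |
| mITT-VF SVR12, no other non-responders | 119/119: 100% (96.9 to 100%) | 119/120: 99.2% (95.4 to 99.9%) |
| mITT-VF SVR12, three other non-responders, all non-virologic | 116/116: 100% (96.8 to 100%) | 116/117: 99.1% (95.3 to 99.9%) |

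In ITT the subject is an SVR12 non-responder either way.

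**The case against.** The best defence is that this is a rare edge case in a study without hypothesis tests. mITT-VF is only a sensitivity population. The SAP also requires listings of subjects excluded from mITT-VF (10.5), of subjects excluded from the relapse denominator and of reasons for non-response (10.7), so a reader could find the case. A local-laboratory value from Day 36 on would close the gap for that subject (6.3). All of this stands and limits the weight of the point. It does not supply the missing category: the listings would show the subject under the wrong label.

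One might answer that a last available post-treatment value ≥ LLOQ counts as relapse. That sentence in 10.1 waives confirmation only; the Final Treatment Visit condition remains.

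Some stronger readings are tempting and are not supported:

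- *Up to about two subjects will be misclassified.* The 0.2 to 1.8 figure counts subjects exposed to the gap, on assumed rates, before asking whether they fail.
- *Any Week 4 value can fall into the gap.* Only Days 2–35 qualify; a value from Days 36–42 can be EOT failure.
- *Every such subject is an on-treatment failure.* If the end-of-treatment sample was drawn late and was < LLOQ, suppression was shown and viraemia followed, which is a relapse pattern. Reinfection is also possible.
- *The same repair should reach anyone treated for 36 days or more.* That would reclassify premature discontinuers, for example Arm A at 36 to 51 days, for whom the SAP has its own category.

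**Conclusion.** The gap is real on the text, and no other rule closes it. It applies to a completer (≥ 52, 77 or 103 days by arm) with no on-treatment value from Day 36 on, a last on-treatment value ≥ LLOQ on Days 2–35 that is not Breakthrough, and viraemia after treatment through the SVR12 window. Arm A is the likeliest place, because one missed or late Week 8 sample is enough; Arms B and C must lack every sample from Day 36 on.

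The expected number is well below one under every assumption tried (0.007 to 0.36), and the primary result is unaffected. The point is therefore minor. It is still worth settling before database lock, because with about 4 non-responders expected a single label visibly changes the virologic failure and mITT-VF results, and always in the favourable direction.

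**What to change.** Add a rule to Section 10.1. It applies to a subject who completed treatment by the existing arm-specific thresholds, has no on-treatment HCV RNA value on or after Day 36, has a Final Treatment value ≥ LLOQ, and has confirmed (or last available) post-treatment HCV RNA ≥ LLOQ through the SVR12 window.

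- The subject counts as a virologic failure for SVR12 and stays in mITT-VF as a failure.
- The subject is Relapse12 if a post-treatment value < LLOQ precedes the viraemia, and on-treatment virologic failure otherwise.
- If a genotype, subtype or clade switch from baseline is shown, the subject is classed as reinfection instead.

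The cost is a short addition to the SAP and the matching programming condition. The downside is that the reported failure count may rise by about one.
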